10.5. Reporting of Adverse Events

Adverse events and Device Deficiencies will be reported according to local regulatory requirements. It is the responsibility of the investigator to abide by the AE/DD reporting requirements stipulated by local law and the Ethics Committee. Reporting requirements in Table 12 have been summarized at the time of CIP creation; however, changes may occur during the course of the study. It is the investigator's responsibility to comply with current reporting requirements.

Refer to section 14.7 for a list of additional required investigator and Medtronic reporting requirements and timeframes.

For AEs/DDs that require immediate reporting, initial reporting may be done by contacting the study sponsor per the sponsor contact information provided in this document. For emergency contact regarding a USADE, SAE and/or SADE, contact a clinical study representative immediately (refer to the study contact list provided in the site's study documents binder/investigator site file or refer to the contact information provided on the title page).

Medtronic Business Restricted

EV ICD Japan Study Clinical Investigation Plan

MDT22010

Version 3.0, 17-OCT-2022

Page 93 of 142

Medtronic

Table 12: Adverse Event Reporting Requirements

Serious Adverse Events (SAEs)	
Investigator submit to:	
Medtronic	Immediately (no later than 72 hours) (Japan GCP Article 68)
Investigators Head of Medical Institution (HOMI)	Submit per IRB reporting requirements
Sponsor submit to:	
Investigators	As for individual report, report to Head of Medical Institution and PI immediately. Head of Medical Institution of each site request the IRB to deliberate them. Or, report to Head of Medical Institution, PI and IRB chairman immediately if needed.
Serious Adverse Device Effects (SADEs)	
Investigator submit to:	
Medtronic	Immediately (no later than 72 hours) (Japan GCP Article 68)
HOMI	Immediately (Japan GCP Article 68)
Sponsor submit to:	
Regulatory authorities	[Life threatening or death] Individual reporting within 15 calendar days after awareness, and [All SADEs] Annually (Enforcement Regulation of the PMDL Article 274- 2)
Investigators HOMI	As for individual report, report to Head of Medical Institution and PI immediately. Head of Medical Institution of each site request the IRB to deliberate them. Or, report to Head of Medical Institution, PI and IRB chairman immediately if needed. As for periodical report, report to Head of Medical Institution and PI annually. Head of Medical Institution of each site request the IRB to deliberate them. Or, report to Head of Medical Institution, PI and IRB chairman annually if needed.
Unanticipated Serious Adverse Device Effects (USADEs)	
Investigator submit to:	
Medtronic	Immediately (no later than 72 hours) (Japan GCP Article 68)
HOMI	Immediately (Japan GCP Article 68)
Sponsor submit to:	
Regulatory authorities	[Life-threatening or death) Individual reporting within 7 calendar days after awareness, [Non-life threatening or death) Individual reporting within 15 calendar days after awareness, and [All USADE] Annually. (Enforcement Regulation of PMDL Article 274-2)
Investigators HOMI	Immediately (Japan GCP Article 28)
Device Deficiencies with SADE potential	
Investigator submit to:	
Medtronic	Immediately (no later than 72 hours) (Japan GCP Article 68)
HOMI	Submit per IRB reporting requirements
Sponsor submit to:	
Regulatory authorities	Within 30 calendar days after awareness and annually (Enforcement Regulation of PMDL Article 274-2)

Medtronic Business Restricted

Investigators HOMI	Immediately per the direction of PMDA and/or annually (Japan GCP Article 28)
-----------------------	--

10.6. Subject Death

All subject deaths must be reported by the investigator to Medtronic on an AE eCRF (AE with fatal outcome) as soon as possible after the investigator first learns of the death. In case of death, there should be one SAE with an outcome of fatal.

A de-identified copy of the death certificate, should be sent to the Medtronic clinical study team. When a death occurs in a hospital, a copy of the death summary report and all relevant hospital records should be sent to Medtronic, if available. If an autopsy is conducted, the autopsy report should also be sent to Medtronic. When the death occurs at a remote site, it is the investigative site's responsibility to attempt retrieval of information about the death. In summary, the following data will be collected:

- Date of death
- Detailed description of death
- Cause of death
- Relatedness to system and/or procedure
- Device interrogation (if available)
- Death summary/hospital records (if available)
- Autopsy report (if available)
- Death certificate (if available)

10.7. Death Classification and Reporting

Sufficient information will be required in order to properly classify the subject's death. The Investigator shall classify each subject death per the following definitions:

Cardiac Death: A death directly related to the electrical or mechanical dysfunction of the heart.

- Sudden Cardiac Death (SCD): Natural death due to cardiac causes, indicated by abrupt loss of consciousness within one hour of the onset of acute symptoms; preexisting heart disease may have been known to be present, but the time and mode of death are unexpected. If time of onset cannot be determined, SCD will alternatively be defined as any unexpected cardiac death occurring out of the hospital or in the emergency room as dead on arrival.
- Non-sudden Cardiac Death: All cardiac deaths that are not classified as sudden deaths, including all cardiac deaths of hospitalized subjects on inotropic support.

Non-cardiac Death: A death not classified as a cardiac death.

Medtronic Business Restricted

Unknown Cardiac Classification: Unknown death classification is intended for use only when there is insufficient or inadequate information to classify the death.

The Clinical Events Committee will also review all deaths and provide an adjudication of the death classification. See section 11.1 for handling events where the adjudication of the investigator and the CEC differ.

10.8. Product Complaint Reporting

The reporting of product complaints is not part of the EV ICD Japan Study and should be done in addition to the AE/DD reporting requirements. It is the responsibility of the investigator to report all product complaints associated with a medical device distributed by Medtronic, regardless of whether they are related to intended use, misuse or abuse of the product. Reporting must be done immediately and via the regular channels for market-released products.

Product Complaint: any written, electronic or oral communication that alleges deficiencies related to the identity, quality, durability, reliability, safety, effectiveness or performance of a medical device that has been placed on the market.

11. Data Review Committees

11.1. Clinical Events Committee

The study will utilize an independent Clinical Events Committee (CEC). At regular intervals, an independent CEC will review events and adjudicate at a minimum all system and procedure-related events. Additionally, the CEC will provide an adjudication of the death classification for all reported deaths.

The CEC will consist of a minimum of three (3) non-Medtronic-employed physicians whose site is not participating in the study, including a CEC chairperson.

Medtronic personnel may facilitate and participate in CEC meetings but will be non-voting members.

For AEs and deaths reviewed by the CEC, Medtronic will provide the CEC with the Investigator's description and supportive documentation (when available). The CEC is responsible for reviewing the Investigator's description and supportive documentation (when available), reviewing applicable definitions, and determining final classifications for all adjudication parameters. For AEs, classification includes system/procedure relatedness and complication (major, minor) or observation. Additionally,

Medtronic Business Restricted

the CEC will provide an adjudication for all reported deaths, including system/procedure relatedness and cardiac relatedness.

If the CEC disagrees with the investigator's classification of the event, the difference will be provided to the investigator. If the investigator agrees with the CEC's adjudication, the eCRF documenting the AE will be updated accordingly.

If the investigator does not agree with the CEC's adjudication classification, both determinations will be provided within the final report; however, the CEC's adjudication will be used for data analysis. The disagreement will also be included in reporting to ethics committees and regulatory authorities, if required.

11.2. Episode Review Committee

An Episode Review Committee (ERC) will be established to evaluate device-treated ventricular episodes according to an ERC Charter. Committee membership, meeting frequency, roles and responsibilities and procedures will also be described in the ERC Charter. Device-treated ventricular episodes in the device episode log with EGM will be reviewed by the ERC and adjudicated based on appropriateness of therapy (shocks and ATP) delivered to subjects and success of the therapy. Inappropriate therapy will be identified based on adjudication rhythm truth and device episode log information.

This committee may include independent physicians and/or Medtronic personnel. The ERC Member list will be under a separate cover and available upon request.

12. Statistical Design and Methods

12.1. General Considerations

Data analysis will be performed by a Medtronic statistician or designee.

The cohort will include all enrolled subjects who undergo the study procedures unless the subject does not complete the required testing, and there are no pre-specified subgroups for assessment. For endpoints involving only measurements collected at follow-up visits, only subjects who complete those visits will be included in the analysis of those endpoints.

A Statistical Analysis Plan will be developed and kept under separate cover and will include a comprehensive description of the statistical methods and reports to be included in the final study report, as well as a description of how missing, unused, and spurious data will be accounted. Any change to the data analysis methods described in the CIP will require an amendment only if it changes

Medtronic Business Restricted

a principal feature of the CIP. Any other change to the data analysis methods described in the CIP, and the justification for making the change, will be described in the clinical study report.

12.2. Sample Size

About 15 and up to 25 subjects will be implanted with the investigational EV ICD system. Enrollment is stopped once 15 subjects have completed the defibrillation protocol testing at implant; but any previously scheduled implant procedures would be allowed to occur. There are no hypotheses for both primary safety and efficacy objectives in this study. The sample size is not pre-specified to satisfy any statistical requirements, but rather to allow for multiple investigational sites enrolling patients and implanting the EV ICD system.

12.3. Primary Objective #1: Safety

Characterize the freedom from major complications related to the EV ICD System and/or procedure at 2 weeks post-implant.

12.3.1. Hypothesis

There are no hypotheses for this objective.

12.3.2. Performance Requirements

Performance requirements are not pre-specified for this objective. The endpoint is defined as a subject's first occurrence of a major complication related to the EV ICD System and/or procedure as determined by the independent Clinical Event Committee (CEC) that occurs on or prior to 2-weeks (14-days) post-implant.

For an adverse event to meet the endpoint, the event must have occurred within 14 days (inclusive) of the EV ICD System implant attempt and be adjudicated by the CEC as being a major complication related to the EV ICD System and/or procedure. Major complications are those complications resulting in:

- Death
- Permanent loss of defibrillation function due to mechanical or electrical dysfunction of the device
- Hospitalization (see Table for Hospitalization definition)
- Prolongation of an existing hospitalization by at least 48 hours
- System revision (reposition, replacement, explant)

Medtronic Business Restricted

12.3.3. Rationale for Performance Criteria

This objective is for the purpose of gathering data pertaining to device safety over the first 2 weeks post-implant. There are no pre-specified performance criteria.

12.3.4. Analysis Methods

Results will be summarized in aggregate using descriptive statistics. The 14-day freedom from major complication rate will be calculated using the Kaplan-Meier method, and the total number of major complications experienced by subjects for whom an implant is attempted will be summarized.

12.3.5. Determination of Subjects/Data for Analysis

All subjects with an implant attempt of the investigational product will be included in the analysis.

12.4. Primary Objective #2: Efficacy

Characterize the EV ICD defibrillation testing success rate at implant.

12.4.1. Hypothesis

There are no hypotheses for this objective.

12.4.2. Performance Requirements

Performance requirements are not pre-specified for this objective. The endpoint, defibrillation testing success, is defined as:

- Single SSVA conversion at 20J, or
- Conversion of two consecutive episodes of SSVA at 30J in final system configuration.

Notes:

- In one of the two consecutive SSVA episodes, up to two 30J shocks are permitted.
- To achieve final system configuration, changing the position of the ICD generator and/or the lead or changing shock polarity is permitted.
- Subjects can return for testing on another day if testing is not fully completed on the day of implant.

Medtronic Business Restricted

12.4.3. Rationale for Performance Criteria

This objective is for the purpose of gathering data pertaining to defibrillation efficacy at implant. There are no pre-specified performance criteria.

12.4.4. Analysis Methods

Results will be summarized in aggregate using descriptive statistics. Subjects will be partitioned by the results of their defibrillation testing (e.g., no rescue shocks required, one rescue shock required), with counts and percentage falling into each subgroup reported. Each subject who completes the defibrillation protocol will be determined to either have successfully met the defibrillation endpoint or not met the endpoint. The EV ICD defibrillation testing success rate at implant will be calculated as the proportion of subjects who successfully met the defibrillation endpoint.

12.4.5. Determination of Subjects/Data for Analysis

All subjects who complete the defibrillation protocol will be included in the analysis.

12.5. Ancillary Objective #1

Characterize appropriate and inappropriate shocks.

12.5.1. Hypothesis

There are no hypotheses for this objective. Spontaneous episodes receiving shocks will be summarized.

12.5.2. Performance Requirements

Performance requirements are not pre-specified for this objective. The endpoint is defined as a shock delivered by the EV ICD. Spontaneous arrhythmic episodes resulting in a shock will be adjudicated to determine the underlying rhythm.

12.5.3. Rationale for Performance Criteria

Due to the minimal number of appropriate and inappropriate shocks expected for spontaneous arrhythmias, this objective is intended to only characterize device performance with regard to sensing ventricular arrhythmias and delivering shocks when the episode either does not self-terminate or is not terminated by ATP. There are no pre-specified performance criteria.

Medtronic Business Restricted

12.5.4. Analysis Methods

Results will be summarized in aggregate using descriptive statistics. All shocks delivered by the device for spontaneous arrhythmias will be partitioned by whether the treated rhythm was a VT/VF episode, and by the specific rhythm of the episode. Both the number of episodes and the number of subjects experiencing such episodes will be reported, as well as the energy delivered. Kaplan-Meier curves for time to first appropriate shock and time to first inappropriate shock may be provided to demonstrate shock incidence.

12.5.5. Determination of Subjects/Data for Analysis

All subjects successfully implanted with an EV ICD having at least one device interrogation post-implant will be included in the analysis. At minimum, all episodes occurring by the date at which all implanted subjects have had the opportunity to be followed for 2 weeks post-implant will be included.

12.6. Ancillary Objective #2

Characterize electrical performance (pacing capture thresholds, pacing impedance, sensing amplitudes) over time.

12.6.1. Hypothesis

There are no hypotheses for this objective. Pacing capture performance, as well as pacing impedance and sensing amplitudes, will be summarized.

12.6.2. Performance Requirements

Performance requirements are not pre-specified for this objective. The endpoints are defined as pacing capture threshold, pacing impedance, and sensing amplitude. The pacing testing will be performed at pre-hospital discharge, as well as visits at 2 weeks, 3- and 6-months post-implant and every 6 months thereafter.

12.6.3. Rationale for Performance Criteria

This objective is for the purpose of characterizing device performance with regard to achieving pacing capture and determining sensing performance over time. There are no pre-specified performance criteria.

Medtronic Business Restricted

12.6.4. Analysis Methods

Results will be summarized in aggregate using descriptive statistics. For each follow-up visit, the proportion of subjects undergoing pacing testing will be reported, as well as the proportion for whom capture is obtained. Mean impedance and R-wave amplitudes will also be reported at each follow-up for which the testing occurs (pre-hospital discharge, 2 weeks, 3- and 6-months post-implant, and every 6 months thereafter).

12.6.5. Determination of Subjects/Data for Analysis

All subjects successfully implanted with an EV ICD having relevant data (pacing tests, impedance, sensing amplitudes) will be included in the analysis of that endpoint at that timepoint.

12.7. Ancillary Objective #3

Characterize extracardiac pacing sensation.

12.7.1. Hypothesis

There are no hypotheses for this objective.

12.7.2. Performance Requirements

Performance requirements are not pre-specified for this objective. The endpoint will be defined as whether pacing therapies were programmed OFF due to pacing sensation.

12.7.3. Rationale for Performance Criteria

There are no pre-specified performance criteria; pacing sensation at follow-up will be summarized and reported.

12.7.4. Analysis Methods

Results will be summarized in aggregate using descriptive statistics. Descriptive statistics will be used to summarize distribution among the subjects who completed each follow-up visit, and whether pacing therapies, specifically ATP, were programmed OFF due to the subject reporting pacing sensation. This objective will be analyzed using data from the pre-hospital discharge, 2 weeks, 3- and 6-month, and long-term visits.

Medtronic Business Restricted

12.7.5. Determination of Subjects/Data for Analysis

For each visit (e.g., PHD, 2 weeks), all subjects successfully implanted with an EV ICD who complete that visit will be included in the analysis.

12.8. Ancillary Objective #4

Characterize asystole pacing.

12.8.1. Hypothesis

There are no hypotheses for this objective, as the purpose of this objective is simply to characterize prevalence of asystole pacing in this population.

12.8.2. Performance Requirements

Performance requirements are not pre-specified for this objective. The endpoint is the amount of pacing for asystole the subject received.

12.8.3. Rationale for Performance Criteria

This objective is for the purpose of characterizing prevalence of need for asystole pacing in this population. There are no pre-specified performance criteria.

12.8.4. Analysis Methods

Descriptive statistics will be used to summarize the number of subjects and amount of asystole pacing experienced during follow-up.

12.8.5. Determination of Subjects/Data for Analysis

All subjects successfully implanted with an EV ICD with at least one device interrogation post-implant will be eligible for the analysis. At minimum, all instances occurring on or before the date at which all implanted subjects have had the opportunity to be followed for 2 weeks post-implant will be included.

12.9. Ancillary Objective #5

Summarize ATP performance with spontaneous arrhythmias.

Medtronic Business Restricted

12.9.1. Hypothesis

There are no hypotheses for this objective, as the purpose is to characterize defibrillation performance through use of ATP.

12.9.2. Performance Requirements

Performance requirements are not pre-specified for this objective. The endpoint is defined as whether a spontaneous ventricular tachycardia episode for which ATP was delivered by the EV ICD was terminated by ATP. Spontaneous arrhythmias will be adjudicated to determine the underlying rhythm and whether they were terminated by ATP.

12.9.3. Rationale for Performance Criteria

It is projected that only a small subset of implanted subjects may experience one or more ventricular arrhythmias during follow-up. Therefore, device performance regarding such episodes will be characterized only. There are no pre-specified performance criteria.

12.9.4. Analysis Methods

Results will be summarized in aggregate using descriptive statistics. All monomorphic and polymorphic ventricular arrhythmias with EGM will be partitioned by whether the treated rhythm received ATP and/or shock, whether it successfully terminated as a result, and by the specific rhythm of the episode (monomorphic vs. polymorphic VT/VF). Both the number of episodes and the number of subjects experiencing such episodes will be reported, as well as the percentage of monomorphic VT episodes successfully terminated by ATP.

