5.3. Minimization of Bias

Selection of subjects, treatment of subjects, and evaluation of study data are potential sources of bias. Methods incorporated in the study design to minimize potential bias include (but are not limited to):

- Subject demographics and comorbidities will be collected at baseline to later assess possible characteristics that may influence endpoints
- Data collection requirements and study procedures will be standardized across all geographies
- To ensure a reasonable distribution of data among sites, the maximum number of enrollments per site will be 12 subjects. Additionally, sites will be encouraged to enroll at least 3 subjects.
- A statistical analysis plan will be developed prior to analyzing data which will document all pre-specified analyses and analysis methods
- All study clinicians will be trained on and required to follow the CIP
- All study clinicians and Medtronic personnel will be trained on their respective aspects of the study using standardized training materials
- An independent Clinical Events Committee (CEC) will be utilized to regularly review and adjudicate reported adverse events
- An Episode Review Committee (ERC) containing independent reviewers will be utilized to review and adjudicate device-treated episodes to determine appropriateness of therapy (shocks and ATP) delivered to subjects
- All sites will use the same version of the CIP and standardized case report forms when possible
- Monitoring visits will be conducted to verify adherence to the CIP and source data.

In summary, potential sources of bias that may be encountered in this clinical study have been considered and minimized by careful study design.

Medtronic Business Restricted

6. Product Description

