Failure to provide effective bradycardia pacing therapy when needed by the subject	
i. Exclusion of subjects with current implantation of a pacemaker, ICD, neurostimulator or any other chronically implanted device which delivers current in the body, that may interfere with therapy delivery
 
ii. Testing during the implant procedure to ensure proper system set-up connections and lead integrity
 
iii. Pacing therapy configuration instructions provided in the CIP and training which help avoid oversensing and resulting failure to deliver pacing therapy when needed (e.g., post-shock)

Medtronic Business Restricted

This document is electronically controlled

CONFIDENTIAL

056-F275, Rev E Clinical Investigation Plan Template

SOP-0818-F01-Rev.E

EV ICD Japan Study Clinical Investigation Plan

MDT22010

Version 3.0, 17-OCT-2022

Page 77 of 142

Medtronic

Risks	Mitigation Strategies
	iv. EV ICD System design verification and end-to-end system design validation ensuring pacing therapy as specified
Delivery of bradycardia pacing therapy at an excessive rate causing symptoms	i. EV ICD System reliability analysis ensuring freedom from failures as specified
Arrhythmia induction (pacing during vulnerable period, proarrhythmic pauses, electrical/mechanical stimulus)	i. An external defibrillation system(s) is required to be present and ready at all times during the implant defibrillation testing procedure. The external defibrillator(s) is to be prepared to be used in case of emergency. ii. EV ICD System reliability analysis ensuring freedom from failures as specified
Acceleration of an existing tachyarrhythmia	i. Defibrillation therapy configuration instructions provided in the protocol and training which help avoid ineffective shock therapy and resulting arrhythmia acceleration ii. EV ICD System design verification and end-to-end system design validation ensuring defibrillation therapy as specified

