10.1. Assessment

10.1.1. Adverse Events Assessment

Adverse Event (AE) definitions are provided in Table 10. All AEs will be collected throughout the study duration, starting at the time the Informed Consent Form is signed. For purposes of reporting, events shall be captured on an AE eCRF or Non Subject AE eCRF.

All instances of shocks delivered by the EV ICD will be considered associated with a reportable AE. Shocks delivered appropriately to treat a ventricular arrhythmia should be noted as treatment delivered within the AE for the ventricular arrhythmia(s) experienced. If shocks are delivered inappropriately due to an EV ICD issue, the issue should be reported as the underlying system related AE.

Reporting of these events to Medtronic will occur on an Adverse Event eCRF, including a description of AE, date of onset of AE, date of awareness of site, treatment, resolution, assessment of both the seriousness and the relatedness to the system and/or procedure. Each AE must be recorded on a separate AE Form. Subject deaths are also required to be reported. Refer to section 10.7 for Subject Death collection and reporting requirements.

Documented pre-existing conditions are not considered AEs unless the nature or severity of the condition has worsened. Worsening may be identified if there is a change in frequency, associated symptoms, or the need for new/additional treatment (e.g., ventricular arrhythmias would be considered worsened if there are new associated symptoms or treatment/shock is warranted). Unavoidable Adverse Events, listed in Table 10 need not be reported unless the adverse event worsens or is present outside the stated timeframe post-implant procedure. Adverse events impacting users or other persons are also reportable during the course of the study.

For AEs that require immediate reporting, initial reporting may be done by phone, fax, or on the eCRF by completing as much information as possible. The AE eCRF must be completed as soon as possible.

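### ATP given for a rhythm that is not VT/VF, with no shock following, is adjudicated for appropriateness but counted in no planned summary, and acceleration after ATP is not separated from simple failure to terminate.

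*Protocol*

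**What the plan says.** **Adjudication.** CIP 5.3 lists the ERC as a bias control that reviews "device-treated episodes to determine appropriateness of therapy (shocks and ATP) delivered to subjects". CIP 11.2 says that episodes are "adjudicated based on appropriateness of therapy (shocks and ATP) delivered to subjects and success of the therapy", and adds: "Inappropriate therapy will be identified based on adjudication rhythm truth and device episode log information". Both sections name ATP alongside shocks.

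**ATP objective (Ancillary Objective #5).** CIP 12.9.2 sets the endpoint: "The endpoint is defined as whether a spontaneous ventricular tachycardia episode for which ATP was delivered by the EV ICD was terminated by ATP". The analysis in CIP 12.9.4, which SAP 7.7.7.4 repeats, is: "All monomorphic and polymorphic ventricular arrhythmias with EGM will be partitioned by whether the treated rhythm received ATP and/or shock". The table is then split by whether the episode ended as a result and by monomorphic versus polymorphic VT/VF. The headline figure is the percentage of monomorphic VT episodes that ATP ended.

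**Shock objective (Ancillary Objective #1).** CIP 12.5.2 and 12.5.4, with SAP 7.7.3.2 and 7.7.3.4, take a delivered shock as the endpoint and split shocks by whether the treated rhythm was VT/VF. The SAP adds one ATP-related item: VT/VF that ATP had already ended but that was shocked anyway.

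**Adverse events.** CIP 10.1.1 states: "All instances of shocks delivered by the EV ICD will be considered associated with a reportable AE". It has no matching rule for ATP.

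**Risk table.** Table 8 in CIP 9.1 has a row for "Acceleration of an existing tachyarrhythmia".

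**The concern.** ATP is one of the advantages that CIP 9.2 claims for this system over subcutaneous ICDs. A fair description of ATP performance covers both how often it ends VT and how often it is delivered when there is no VT to end. The plan collects the judgement needed for the second part, because the ERC rules on the appropriateness of ATP, but no planned summary uses that judgement. Shocks get an appropriate/inappropriate split and ATP does not, and neither document explains the difference.

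In a study this small, a single episode of inappropriate ATP would be worth reporting. If the count is not planned, whether it appears is decided after the data have been seen. In the same way, a reader of the planned table could not tell an ATP sequence that did nothing from one after which the VT accelerated.

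**Working it through.** No formula applies, and the plan states no figure to reproduce. The check is to follow each kind of adjudicated episode through the planned analyses.

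1. **Shock, appropriate or inappropriate.** Counted in Ancillary Objective #1 by rhythm, in episodes and subjects, and tied to a reportable adverse event under CIP 10.1.1. Covered.
2. **ATP for true VT/VF, ended or not.** Counted in Ancillary Objective #5. Covered.
3. **ATP for a non-VT/VF rhythm, followed by a shock.** The shock is counted in Ancillary Objective #1 as treatment of a rhythm other than VT/VF. Covered through the shock, although the ATP itself is not.
4. **ATP for a non-VT/VF rhythm, no shock.** Outside Ancillary Objective #1, because there is no shock. Outside Ancillary Objective #5, because the rhythm is not a ventricular arrhythmia. Not covered by either.
5. **ATP for VT that then accelerates.** Stays in Ancillary Objective #5 as not terminated, or as ATP plus shock. If shocked, it is also counted in Ancillary Objective #1 and tied to a reportable adverse event. Counted, but not identified as acceleration.

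Two readings that might close case 4 were checked.

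- *Could the ventricular arrhythmias of CIP 12.9.4 mean episodes that the device labelled ventricular, true or false?* The surrounding text points the other way. CIP 12.9.2 has the underlying rhythm adjudicated, 12.9.4 gives only monomorphic and polymorphic VT/VF as rhythm categories, and 12.9.5 describes the data as VT/VF episodes. A false detection has no row.
- *Does the SAP add the missing count?* No. Its one addition on ATP (SAP 7.7.3.4) concerns shocks delivered after ATP had already succeeded.

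On case 5, CIP 11.2 says that the ERC adjudicates appropriateness and success. Neither document defines acceleration or says that the ERC records it.

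**The case against.** The strongest reply is that little is truly lost. This is an ancillary objective with no hypothesis and no performance criterion. CIP 12.9.3 expects only a small subset of subjects to have ventricular arrhythmias, and with so few subjects each episode can be described individually. SAP 7.3 puts all available data into listings and tabulations, and SAP section 3 says that the plan does not limit the analyses. These points are right about importance, and they set the size of the finding. They do not remove it: general clauses permit an ATP summary but do not plan one.

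Three stronger readings are tempting, and the documents do not support them.

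- **That acceleration after ATP is lost.** It is not. Case 5 shows that the episode stays in the ATP table and, if shocked, in the shock table. Only the label is missing. The acceleration row in Table 8 also does not establish an ATP-specific risk, because its mitigation text refers to ineffective shock therapy.
- **That adverse-event reporting offers no backstop.** It offers a partial one. CIP 10.1.1 treats a worsened pre-existing arrhythmia as reportable, including one with new symptoms. CIP 10.1.2 lists persistent sensing problems as a possible device deficiency, and SAP 7.8 reports deficiencies individually. These routes can miss asymptomatic inappropriate ATP, but they exist.
- **That the subcutaneous-ICD cohorts in Appendix D give the frequency.** They report inappropriate shocks in 41/314 = 13.1% and 15/118 = 12.7% of patients. Those are shocks, which Ancillary Objective #1 would show here. They come from a different type of system, over 180 days and up to 18 months, whereas the planned report follows the 2-week visit. ATP programming at discharge is also left to the physician (CIP Table 5). No rate for ATP-only false detections can be taken from them.

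**Conclusion.** The point holds in a narrow form. No planned summary counts ATP delivered for a non-VT/VF rhythm when no shock follows, although the ERC is to judge exactly that. Acceleration after ATP is counted only as non-termination or as ATP plus shock.

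The size is minor. No primary objective, sample-size statement or decision rule is touched, and no expected number of affected subjects can be derived from the documents. What is at stake is the balance of one descriptive summary, which as written reports termination and not inappropriate use.

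The conclusion assumes that the ERC reviews false detections as well as true ventricular episodes. CIP 11.2 implies this, because inappropriate therapy is to be identified by comparing the adjudicated rhythm with the device log. It also assumes that the ventricular arrhythmias in CIP 12.9.4 are adjudicated ones, as the rhythm categories there indicate.

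**What to change.** In CIP 12.9.4 and SAP 7.7.7.4, start the ATP summary from all ERC-adjudicated spontaneous episodes in which ATP was delivered, whatever the rhythm. Report the number of episodes and of subjects by adjudicated rhythm, and include non-VT/VF as inappropriate ATP, broken down by cause (for example supraventricular rhythm or oversensing). Bring the data descriptions in CIP 12.9.5 and SAP 7.7.7.5 into line, since they now refer to VT/VF episodes. Leave the monomorphic VT termination percentage unchanged.

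Optionally, split VT/VF that ATP did not end into unchanged versus accelerated or degenerated.

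**Cost.** The main change adds rows to one table from episodes that the ERC already adjudicates, with no new visit, test or hypothesis. The ATP summary may look slightly less favourable. The optional split costs more, because it needs a written definition of acceleration and one added field in the ERC's review.
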